6.1 Unanticipated Problems

501 Site investigators will promptly report to the Coordinating Center and Sponsor on an eCRF all
502 unanticipated problems meeting the criteria below. For this protocol, an unanticipated problem is an
503 incident, experience, or outcome that meets all of the following criteria:

- 504 • Unexpected (in terms of nature, severity, or frequency) given (a) the research procedures that are
505 described in the protocol related documents, such as the IRB-approved research protocol and
506 informed consent document; and (b) the characteristics of the subject population being studied
- 507 • Related or possibly related to participation in the research (possibly related means there is a
508 reasonable possibility that the incident, experience, or outcome may have been caused by the
509 procedures involved in the research)
- 510 • Suggests that the research places participants or others at a greater risk of harm than was previously
511 known or recognized (including physical, psychological, economic, or social harm)

512 The Coordinating Center will report to the IRB all unanticipated problems not directly involving a
513 specific site such as unanticipated problems that occur at another participating entity such as a pharmacy
514 or laboratory. These instances must be reported to the study IRB within seven calendar days of
515 recognition. The Sponsor will report to the appropriate regulatory authorities if the IRB determines that
516 the event indeed meets the criteria of an Unanticipated Problem requiring additional reporting.

517

6.2 Adverse Events

518

6.2.1 Definitions

519 **Adverse Event (AE)**: Any untoward medical occurrence (including laboratory findings) associated with
520 study procedures, the use of a device, biologic in a study participant, including any comparator used,
521 irrespective of the relationship between the adverse event and the device(s) under investigation (referred
522 to as *Adverse Reaction* when caused by a drug).

523 **Serious Adverse Event (SAE)**: Any untoward medical occurrence that meets at least one of the following:

- 524 • Results in death.
- 525 • Is life-threatening; (a non-life-threatening event which, had it been more severe, might have become
526 life-threatening, is not necessarily considered a serious adverse event).
- 527 • Requires inpatient hospitalization or prolongation of existing hospitalization.
- 528 • Results in persistent or significant disability/incapacity or substantial disruption of the ability
529 to conduct normal life functions (sight threatening).
- 530 • Is a congenital anomaly or birth defect.
- 531 • Is considered a significant medical event by the investigator based on medical judgment (e.g., may
532 jeopardize the participant or may require medical/surgical intervention to prevent one of the outcomes
533 listed above).

534 **Unanticipated Adverse Device Effect (UADE)**: Any serious adverse effect on health or safety or any
535 life-threatening problem or death caused by, or associated with, a device, if that effect, problem, or death
536 was not previously identified in nature, severity, or degree of incidence in the investigational plan or

537 application (including a supplementary plan or application), or any other unanticipated serious problem
538 associated with a device that relates to the rights, safety, or welfare of participants (21 CFR 812.3(s)).

539 **Adverse Device Effect (ADE):** Any untoward medical occurrence in a study participant which the device
540 may have caused or to which the device may have contributed (Note that an Adverse Event Form is to be
541 completed in addition to a Device Issues Form, unless excluded from reporting as defined in section
542 6.2.2).

543 **Comparator:** Medical device, therapy (e.g. active treatment, normal clinical practice), placebo or no
544 treatment, used in the control group in a clinical investigation. (ISO 14155:2020)

545 **Device Complaints and Malfunctions:** A device complication or complaint is something that happens
546 to a device or related to device performance, whereas an adverse event happens to a participant. A device
547 complaint may occur independently from an AE, or along with an AE. An AE may occur without a
548 device complaint or there may be an AE related to a device complaint. A device malfunction is any
549 failure of a device to meet its performance specifications or otherwise perform as intended.
550 Performance specifications include all claims made in the labeling for the device. The intended
551 performance of a device refers to the intended use for which the device is labeled or marketed.
552 (21 CFR 803.3). Note: for reporting purposes, sites will not be asked to distinguish between device
553 complaints and malfunctions.

554 **Use Error:** User action or lack of user action while using the medical device (3.34) that leads to a
555 different result than that intended by the manufacturer or expected by the user. Includes the inability of
556 the user to complete a task. Use errors can result from a mismatch between the characteristics of the user,
557 user interface, task or use environment. Users might be aware or unaware that a use error has occurred.
558 An unexpected physiological response of the patient is not by itself considered a use error. A malfunction
559 of a medical device that causes an unexpected result is not considered a use error. (ISO 14155:2020)

560 **6.2.2 Reportable Adverse Events**

561 A reportable adverse event includes all events meeting the definition of an adverse event, except for the
562 following:

- 563 • Hypoglycemia and hyperglycemia not meeting the criteria below will not be recorded as adverse
564 events unless associated with an Adverse Device Effect or discontinuation of the study device or
565 study drug.
- 566 • Skin reactions from sensor or pump infusion set placement are only reportable if severe and/or
567 required treatment.

568 All reportable AEs—whether volunteered by the participant, discovered by study personnel during
569 questioning, or detected through physical examination, laboratory test, or other means—will be reported
570 on an AE form online. Each AE form is reviewed by the Medical Monitor to assess safety and to verify
571 the coding and the reporting that is required.

572 **6.2.3 Hypoglycemic Events**

573 Hypoglycemia is only reportable as an adverse event when one of the following criteria is met:

- 574 • a hypoglycemic event occurred meeting the following definition of severe hypoglycemia: the event
575 required assistance of another person due to altered consciousness, and required another person to
576 actively administer carbohydrate, glucagon, or other resuscitative actions. This means that the
577 participant was impaired cognitively to the point that he/she was unable to treat himself/herself, was
578 unable to verbalize his/ her needs, was incoherent, disoriented, and/or combative, or experienced
579 seizure or loss of consciousness. These episodes may be associated with sufficient neuroglycopenia to
580 induce seizure or loss of consciousness. If glucose measurements are not available during such an
581 event, neurological recovery attributable to the restoration of glucose to normal is considered
582 sufficient evidence that the event was induced by a low glucose concentration.
- 583 • evaluation or treatment was obtained at a health care provider facility for an acute event involving
584 hypoglycemia, or the participant contacted the site and received guidance following the occurrence of
585 an acute event involving hypoglycemia

586 When a severe hypoglycemia event occurs (as defined above), an Adverse Event Form should be
587 completed. Severe hypoglycemia events should be considered to be serious adverse events with respect to
588 reporting requirements. When a severe hypoglycemia event occurs during use of a study device, it
589 generally will be considered to be unrelated to the device (per section 6.2.5) if the device functioned as
590 intended and there does not appear to be a flaw in how the device is intended to function.

591 **6.2.4 Hyperglycemic/Ketotic Events**

592 Hyperglycemia is only reportable as an adverse event when one of the following criteria is met:

- 593 • the event involved DKA, as defined by the Diabetes Control and Complications Trial (DCCT) and
594 described below
- 595 • evaluation or treatment was obtained at a health care provider facility for an acute event involving
596 hyperglycemia or ketosis, or the participant contacted the site and received guidance on how to
597 manage the hyperglycemia/ketosis
- 598 • blood ketone level ≥ 0.6 mmol/L, even if there was no communication with a health care provider at
599 the time of the event

600 Hyperglycemic events are classified as DKA if the following are present:

- 601 • Symptoms such as polyuria, polydipsia, nausea, or vomiting;
- 602 • Serum ketones > 1.5 mmol/L or large/moderate urine ketones;
- 603 • Either arterial blood pH < 7.30 or venous pH < 7.24 or serum bicarbonate (or CO₂) < 15 ; and
- 604 • Treatment provided in a health care facility

605 When a hyperglycemia/ketotic event qualifies as an SAE as defined in section 6.2.1, an Adverse Event
606 Form should be completed. Events meeting DKA criteria should be considered to be serious adverse
607 events with respect to reporting requirements. Hyperglycemia events not meeting criteria for DKA

608 generally will not be considered as serious adverse events unless one of the SAE criteria in section 6.2.1
609 is met.

610 DKA can occur at “euglycemic” glucose levels less than 250 mg/dL, and may occur more commonly in
611 individuals taking adjuvant medications for glucose control such as SGLT-2 inhibitors. This should be
612 reported as a DKA event if it occurs.

613 When a hyperglycemia/DKA event occurs during use of a study device, it generally will be considered to
614 be unrelated to the device (per section 6.2.5) if the device functioned as intended and there does not
615 appear to be a flaw in how the device is intended to function.

616 **6.2.5 Relationship of Adverse Event to Study Investigational Device**

617 The study investigator will assess the relationship of any adverse event to the study device or study drug.
618 The Medical Monitor also will make this assessment, which may or may not agree with that of the study
619 investigator. Reporting requirements will be based on the Medical Monitor’s assessment.

620 To ensure consistency of adverse event causality assessments, investigators should apply the following
621 general guidelines when determining whether an adverse event is related to a study device or study drug:

622 **Unrelated:** The AE is clearly not related to a study drug/device and a likely alternative etiology exists
623 such as an underlying disease, environmental or toxic factors or other therapy.

624 **Unlikely Related:** The AE does not follow a reasonable temporal sequence during or after use of study
625 drug/device and a more likely alternative etiology exists such as an underlying disease, environmental or
626 toxic factors, or other therapy.

627 **Possibly Related:** The AE occurred in a reasonable time during or after use of study drug/device; but
628 could be related to another factor such as an underlying disease, environmental or toxic factors, or other
629 therapy; and there is a possible, though weak, scientific basis for establishing a causal association
630 between the AE and the study drug/device.

631 **Probably Related:** The AE occurred in a reasonable time during or after use of study drug/device; is
632 unlikely to be related to another factor such as an underlying disease, environmental or toxic factors, or
633 other therapy; and there is a plausible, though not strong, scientific basis for establishing a causal
634 association between the AE and the study drug/device.

635 **Definitely Related:** The AE occurred in a reasonable time during or after use of study drug/device;
636 cannot be explained by another factor such as an underlying disease, environmental or toxic factors, or
637 therapy; and there is a strong scientific basis for establishing a causal association between the AE and the
638 study drug/device.

639 Events determined to be *Possibly Related*, *Probably Related*, or *Definitely Related* will be considered
640 ‘Related’ with respect to any required IRB and FDA reporting.

641 **6.2.6 Severity (Intensity) of Adverse Events**

642 The severity (intensity) of an adverse event will be rated on a three-point scale: (1) mild, (2) moderate,
643 or (3) severe. A severity assessment is a clinical determination of the intensity of an event. Thus, a severe
644 adverse event is not necessarily serious. For example, itching for several days may be rated as severe, but
645 may not be clinically serious.

646 **MILD:** Usually transient, requires no special treatment, and does not interfere with the participant’s daily
647 activities.

648 MODERATE: Usually causes a low level of inconvenience, discomfort or concern to the participant
649 and may interfere with daily activities, but is usually ameliorated by simple therapeutic measures and
650 participant is able to continue in study.

651 SEVERE: Interrupts a participant's usual daily activities, causes severe discomfort, may cause
652 discontinuation of study device, and generally requires systemic drug therapy or other treatment.

653 **6.2.7 Expectedness**

654 For a serious adverse event that is considered possibly related to study device, the Medical Monitor will
655 classify the event as unexpected if the nature, severity, or frequency of the event is not consistent with the
656 risk information previously described in the protocol, labeling, or Investigator Brochure.

657 **6.2.8 Coding of Adverse Events**

658 Adverse events will be coded using the MedDRA dictionary.

659 **6.2.9 Outcome of Adverse Events**

660 The outcome of each reportable adverse event will be classified by the investigator as follows:

- 661 • RECOVERED/RESOLVED – The participant recovered from the AE/SAE without sequelae. Record
662 the AE/SAE stop date.
- 663 • RECOVERED/RESOLVED WITH SEQUELAE – The event persisted and had stabilized without
664 change in the event anticipated. Record the AE/SAE stop date.
- 665 • FATAL – A fatal outcome is defined as the SAE that resulted in death. Only the event that was the
666 cause of death should be reported as fatal. AEs/SAEs that were ongoing at the time of death;
667 however, were not the cause of death, will be recorded as “resolved” at the time of death.
- 668 • NOT RECOVERED/NOT RESOLVED (ONGOING) – An ongoing AE/SAE is defined as the event
669 was ongoing with an undetermined outcome.

670 *An ongoing outcome will require follow-up by the site in order to determine the final outcome
671 of the AE/SAE. The outcome of an ongoing event at the time of death that was not the cause of
672 death, will be updated and recorded as “resolved” with the date of death recorded as the stop
673 date.*

- 674 • UNKNOWN – An unknown outcome is defined as an inability to access the participant or the
675 participant's records to determine the outcome (for example, a participant that was lost to follow-up).

676 If any reported adverse events are ongoing when a participant completes the study (or withdraws),
677 adverse events classified as UADEs or related SAEs or SUSARs will be followed until they are either
678 resolved, or have no prospect of improvement or change, even after the participant has completed all
679 applicable study visits/contacts. For all other adverse events, data collection will end at the time the
680 participant completes the study. Note: participants should continue to receive appropriate medical care
681 for an adverse event after their participation in the study ends.

682 **6.3 Reportable Device Issues**

683 All UADEs and ADEs as defined in section 6.2.1 will be reported as both a ‘device issues’ and ‘adverse
684 event’, except for skin reactions from CGM sensor placement or pump infusion set placement that do not
685 require pharmacologic treatment.

686 Device complaints and device malfunctions will be reported except in the following circumstances.
687 These occurrences are expected and will not be reported on a Device Issue Form assuming criteria for
688 a UADE or ADE have not been met:

- 689 • CGM sensor lasting fewer days than expected per manufacturer
- 690 • CGM tape adherence issues
- 691 • Pump infusion set insertion lasting fewer days than expected per manufacturer
- 692 • Battery lifespan deficiency due to inadequate charging or extensive wireless communication
- 693 • Intermittent device component disconnections/communication failures not requiring system
694 replacement or workaround/resolution not specified in user guide/manual.
- 695 • Device issues clearly addressed in the user guide manual that do not require additional
696 troubleshooting

697 **6.4 Timing of Event Reporting**

698 SAEs possibly related to a study device, study drug, or study participation and UADEs must be reported
699 by the site to the Sponsor within 1 working day of the site becoming aware of the event. This can occur
700 via phone or email, or by completion of the appropriate eCRFs as applicable. If the form(s) are not
701 initially completed, they should be completed as soon as possible after there is sufficient information to
702 evaluate the event. All other reportable ADEs and other reportable AEs should be submitted by
703 completion on the eCRF(s) within 7 days of the site becoming aware of the event.

704 The Sponsor will notify all participating investigators of any adverse event that is serious, related, and
705 unexpected. Notification will be made within 10 working days after the Sponsor becomes aware of the
706 event.

707 Each principal investigator is responsible for reporting serious study-related adverse events and abiding
708 by any other reporting requirements specific to his/her Institutional Review Board or Ethics Committee.

709 Upon receipt of a qualifying event, the Sponsor will investigate the event to determine if a UADE has
710 occurred, and if indicated, report the results of the investigation to all overseeing IRBs, and the FDA
711 within 10 working days of the Sponsor becoming aware of the UADE per 21CFR 812.46(b). The Sponsor
712 must determine if the UADE presents an unreasonable risk to participants. If so, the Sponsor must ensure
713 that all investigations, or parts of investigations presenting that risk, are terminated as soon as possible but
714 no later than 5 working days after the Sponsor makes this determination and no later than 15 working
715 days after first receipt notice of the UADE.

716 The investigators are also required to report, without unjustified delay, all device complaints and
717 malfunctions that could have led to a UADE, including device complaints and malfunctions, irrespective
718 of whether an adverse event occurred.

719 **6.5 Safety Oversight**

720 The study Sponsor's Medical Director will serve as Medical Monitor, and will review all adverse events,
721 including all cases of severe hypoglycemia and DKA, and adverse device events that are reported during
722 the study. SAEs typically will be reviewed within 1 working day of reporting. Other AEs typically will be
723 reviewed on a weekly basis, as per the study safety management plan.

724 The Medical Monitor will determine if the events require expedited reporting to FDA, IRB and/or all
725 participating sites. In addition, the Medical Monitor will confirm the MedDRA code assigned and
726 adjudicate events for relatedness to the study procedure and investigational device, assess seriousness and
727 severity, and determine if the event is anticipated or unanticipated. Both the investigator's and

728 Medical Monitor's assessments will be recorded, however, the adjudication decision of the Medical
729 Monitor will be used for the final classification of events, including relatedness to the study procedures
730 and/or the investigational device, for the determination of safety endpoints and for all regulatory reports,
731 product labeling, and publications or presentations.

732 **6.6 Stopping Criteria**

733 **6.6.1 Participant Discontinuation of Study Device**

734 In the case of an unanticipated system malfunction resulting in a severe hypoglycemia or DKA event
735 (or a malfunction that could have led to severe hypoglycemia or DKA), use of the study device will be
736 suspended for that participant while the problem is diagnosed. The UADE will be reported to the IRB and
737 FDA. After assessment of the problem and any correction, use of the study device will not be restarted
738 until approval is received from the IRB and FDA.

739 In the absence of a device malfunction, use of the study device by a participant will be discontinued if
740 any of the following occur:

- 741 • The investigator believes it is unsafe for the participant to continue on the intervention. This could be
742 due to the development of a new medical condition or worsening of an existing condition; or
743 participant behavior contrary to the indications for use of the device that imposes on the participant's
744 safety
- 745 • The participant requests that the treatment be stopped
- 746 • Participant pregnancy
- 747 • Two distinct episodes of DKA as defined in section 6.2.4
- 748 • Two distinct severe hypoglycemia events as defined in section 6.2.3
- 749 • One episode of DKA as defined in section 6.2.4 and one severe hypoglycemia event as defined in
750 section 6.2.3

751 Each DKA or severe hypoglycemia event will be reviewed by the Medical Monitor with respect to
752 determination of cause and whether the occurrence of the event can be attributed to use of the study
753 device or study drug.

754 An additional requirement for continued study device use following a single DKA or severe
755 hypoglycemia event will be that the site investigator believes that the event is unlikely to recur and that
756 it is safe for the participant to continue to use the system. Additionally, if the Medical Monitor determines
757 that the occurrence of the event indicates that it is not safe for the participant to continue to use the study
758 device, use will be discontinued.

759 **6.6.2 Criteria for Suspending or Stopping Overall Study**

760 In addition to the suspension of device use due to a UADE as described in section 6.6.1, study activities
761 could be similarly suspended if the manufacturer of any constituent study device requires stoppage of
762 device use for safety reasons (e.g. product recall). The affected study activities may resume if the
763 underlying problem can be corrected by a protocol or system modification that will not invalidate the
764 results obtained prior to suspension.

765 Closed-loop system use will also be suspended if there are three or more cases of severe hypoglycemia or
766 three or more cases of hyperglycemia/ketotic events qualifying as SAEs across the entire study in
767 participants who have initiated Control-IQ technology use. The IRBs and FDA will be notified. After
768 assessment of the problem and any corrections are implemented, use of the closed-loop system may be
769 restarted if approval is received from the IRBs and FDA.

770

771

Confidential

Contains trade secrets and/or confidential information exempt from disclosure from 21 CFR 20.61

Chapter 7: Miscellaneous Considerations

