²Pregnancy test does not need to be repeated if screening and Control-IQ training visits are performed on the same day.

1 Chapter 1: Background Information

2 1.1 Introduction

3 1.1.1 Disease Background

4 Type 1 diabetes affects 1.25 million people in the United States. Approximately 70% of individuals with
5 type 1 diabetes report poor metabolic control, and do not meet the American Diabetes Association's
6 recommended goal of hemoglobin A1c (HbA1c) level of 7.0%. These findings indicate the need for better
7 approaches to type 1 diabetes management.

8 1.1.2 Tandem X2 Insulin Pump with Control-IQ Technology

9 The Tandem X2 insulin pump with Control-IQ technology is an FDA-approved closed-loop control
10 (CLC) system based on the control algorithm developed and initially tested in the University of
11 Virginia's DiAs system and then implemented in the inControl system (TypeZero, Technologies, Inc.).
12 Use of the Control-IQ system has been extensively tested in adults and children with type 1 diabetes
13 (T1D), demonstrating its efficacy and safety when used with insulin lispro (Humalog) or insulin aspart
14 (Novolog).^{1,2} The system is currently approved for ages 6 years and older and use in younger children is
15 currently being studied (clinical trials.gov NCT04796779). There are over 150,000 users of the
16 system since it became commercially available in 2020. A recent evaluation of real-world use of the
17 system in 9,451 users age ≥ 6 years with at least 12 months of system use found results comparable to
18 those found in the randomized trials.³

19 Since the initial approval of the system, modifications have been made in the software, which is referred
20 to as version 1.5. These modifications include modest usability improvements and other enhancements
21 intended to further reduce risk. The Control-IQ 1.5 system also removes the 3 units/hr basal clipping,
22 allowing the pump to deliver programmed user profile basal rates above 3 units/hr when 30 minute
23 predicted glucose is expected to be in the target range. This has the potential to further improve outcomes
24 in individuals using basal rates at or above this threshold.

25 1.2 Rationale

26 The objective of this single-arm, prospective study is to assess safety and explore glycemic outcomes
27 associated with use of the Control-IQ 1.5 system in adults with type 1 diabetes using basal rates > 3
28 units/hr for at least part of the day.

29 1.3 Potential Risks and Benefits

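### The presumption in 6.2.3 and 6.2.4 that severe hypoglycemia and DKA are generally unrelated to the device has no basis in 6.2.5, and it can move such events from the 1-working-day to the 7-day reporting limit

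*Combined protocol and SAP*

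**What the plan says.** **Presumption.** Section 6.2.3 states that severe hypoglycemia during use of a study device "generally will be considered to be unrelated to the device (per section 6.2.5) if the device functioned as" "intended and there does not appear to be a flaw in how the device is intended to function". Section 6.2.4 repeats the rule for hyperglycemia and DKA: such an event will generally "be unrelated to the device (per section 6.2.5) if the device functioned as intended and there does not" appear to be a flaw in the intended function. Both sections treat the events (severe hypoglycemia, and events meeting the DKA criteria) as SAEs for reporting.

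**Causality categories.** Section 6.2.5 defines Unrelated as: "The AE is clearly not related to a study drug/device and a likely alternative etiology exists". Possibly Related begins "The AE occurred in a reasonable time during or after use of study drug/device; but" and goes on to allow that another factor, such as underlying disease, could explain the event. It asks only for a possible, though weak, scientific basis for causation. The Medical Monitor makes a separate assessment, and that assessment governs reporting requirements.

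**Reporting limits.** Section 6.4 sets the short limit by relatedness: "SAEs possibly related to a study device, study drug, or study participation and UADEs must be reported" within 1 working day of site awareness. Other reportable AEs have 7 days. Section 6.5 says the Medical Monitor typically reviews SAEs within 1 working day of their being reported.

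**Suspension.** Section 6.6.2 reads "Closed-loop system use will also be suspended if there are three or more cases of severe hypoglycemia or" three or more hyperglycemic/ketotic SAEs. It sets no relatedness condition.

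**The concern.** The presumption cites 6.2.5 but applies a test that 6.2.5 does not contain, so one event can receive two different ratings depending on which section the investigator follows.

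This matters more here than in most device studies. Section 1.1.2 describes the removal of the 3 units/hr basal clipping as a feature of version 1.5, and section 8.2 refers to use of the system with that feature removed. Harm caused by the change could occur while the device does exactly what it was designed to do. A test that starts from whether the device worked as designed is poorly suited to detecting such harm.

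Two things are at stake. One is the relatedness classification, which under 6.2.7 and 6.4 also decides whether expectedness is assessed and whether other investigators are notified. The other is how soon the sponsor learns of an event that counts toward suspending the study.

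**Working it through.** The plan gives no figure on this point. The check sets the sections side by side and then bounds the delay.

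**Step 1: the same event under both rules.** Take a severe hypoglycemia event during automated delivery, with no malfunction and no evident design flaw.

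| Question | 6.2.3 / 6.2.4 | 6.2.5 |
|---|---|---|
| Is device function a criterion? | Yes | No |
| What does Unrelated need? | Device worked as designed, no apparent flaw | Clear absence of relation and a likely alternative cause |
| Effect of an event during use | None stated | Reasonable timing supports Possibly Related; Unlikely Related needs the absence of a reasonable time sequence |
| Usual rating | Unrelated | Possibly Related, if a weak causal basis exists |

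The ADE definition in 6.2.1 agrees with 6.2.5: it is enough that the device may have contributed, and no malfunction is required.

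**Step 2: the reporting limit that follows (6.4).**

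- Possibly related to device, study drug or study participation, or a UADE: 1 working day.
- Unrelated to all three and not a UADE: 7 days, even though the event is always an SAE for reporting.

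The presumption settles only the device element. An event loses the short limit only if it is also rated unrelated to study drug and to participation.

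**Step 3: does another provision close the gap?** The Medical Monitor can overrule the site's rating, but the review target in 6.5 runs from reporting, so it cannot shorten the interval before the report. The count in 6.6.2 ignores relatedness, yet a case cannot be counted centrally until it is reported.

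**Step 4: size of the delay.** Inputs: 7 days and 1 working day (6.4); 30 participants (8.2, the minimum number of completers); 13 weeks of use (Protocol Summary).

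- Longest delay per event: 7 − 1 = 6 days.
- Extra closed-loop use if the third case is the late one and 30 participants are on the device: 6 × 30 = 180 participant-days, and 180 / 365.25 = 0.49 person-years.
- For scale, planned use by 30 completers is 30 × 13 × 7 = 2,730 participant-days, and 180 / 2,730 = 6.6%.
- If the working day spans a weekend (assumed here as 3 calendar days), the delay falls to 7 − 3 = 4 days, or 4 × 30 = 120 participant-days.

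**Step 5: what does not depend on relatedness.** The severe hypoglycemia and DKA rates in 8.3 and the suspension count in 6.6.2 carry no relatedness condition.

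**The case against.** The strongest defence is that the presumption is mild and well guarded. It says generally, so it can be rebutted, and its second condition lifts it when the intended function itself looks flawed. The categories in 6.2.5 are themselves offered as general guidelines. The Medical Monitor reviews every severe hypoglycemia and DKA event, and 6.6.1 requires a determination of cause for each. After a single event, continued use already depends on the site investigator's judgment that it is safe, whatever the sponsor-reporting limit.

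Much of this stands, and it rules out several stronger conclusions that a reader might infer:

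- *That every event without a malfunction is classed as unrelated.* The text says generally and adds the no-flaw condition.
- *That these events automatically leave the 1-working-day limit.* Section 6.4 also covers study drug and study participation. An event tied to a meal or exercise challenge, or to the study-supplied insulin if that counts as study drug (the term is not defined), can stay on the short limit.
- *That the presumption drives the UADE count toward zero.* A UADE must be unidentified beforehand in nature, severity or degree of incidence. Hypoglycemia, hyperglycemia with ketonemia, and wrong delivery are already listed risks in 1.3.1, so most such events would not qualify however they were rated. Malfunction cases are handled separately in 6.6.1.
- *That exposure should be computed for 60 participants.* Sixty is the ceiling on screening, not a number on the device.

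The defence does not remove the conflict. The protocol gives no criterion for an apparent flaw, and a single event will seldom reveal one. The safeguards that rest on the Medical Monitor begin only once the report arrives.

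**Conclusion.** The point holds as a conflict between sections with a limited practical consequence. The presumption can class as unrelated an event that 6.2.5 would class as possibly related. An event rated unrelated to device, study drug and participation may then reach the sponsor up to 7 days after site awareness, while the suspension rule counts it regardless.

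The harm is to reporting speed and to the relatedness classification. It does not reach the primary severe hypoglycemia and DKA rates, and it hardly touches the UADE count.

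The bound of about 6 days per event and about 180 participant-days assumes that the site uses the full 7 days, that the working day is one calendar day, and that 30 participants are on the device at once. With staggered enrollment or prompt sites the figure is smaller.

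**What to change.** 1. In 6.4, place all severe hypoglycemia and DKA events on the 1-working-day limit, whatever their relatedness.
2. Reconcile 6.2.3 and 6.2.4 with 6.2.5 by removing the presumption, so that each event is judged on the 6.2.5 categories. Writing the device-function test into 6.2.5 would also end the contradiction, but it would keep a test that is weak against harm from intended function.

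Optionally, tabulate the investigator's and the Medical Monitor's classifications side by side. Section 6.5 already has both recorded, although it makes the Medical Monitor's decision final.

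The cost is a few sentences of protocol wording and no new data. Sites will report some events sooner, and more events may be classed as related.
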